3. HYPOTHESES AND OBJECTIVES

3.1. HYPOTHESIS:

Levobupivacaine has advantages over Ropivacaine in the combined blockade (PENG - pericapsular nerve group- and the femoral lateral cutaneous nerve -BNFCL-) in hip fractures of the elderly, since a better analgesic control, similar latency period, and a longer analgesic duration are obtained.

3.2. OBJECTIVES:

3.2.1. MAIN:

- To compare the analgesic efficacy of both local anaesthetics in the regional blockade of hip fracture surgery.

3.2.2. SECONDARY:

- To describe the behavior of this combined technique in hip fractures, establishing latency of onset and duration of analgesia.
- Describe the side effects derived from the described combined technique. To validate in our population, especially in patients with cognitive impairment, the usefulness of the analgesic scales chosen.

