6.7. MEASUREMENTS

- Demographic variables: age, sex, weight, height, comorbidity (ASA grade).
- Variables related to the injury: subcapital fracture, pectrochanteric, subpectrochanteric or others.
- Variables related to the type of surgery: partial hip arthroplasty, endomedullary nailing or others. Duration of surgery.
- Variables related to the response:
 - Latency: evaluated by analgesic scales up to 10 minutes.
 - Analgesic scales: EVN, Algoplus and PAINAD at rest and in activity. They will be carried out upon the patient's arrival at the operating room, continuous until 10 minutes after the nerve block, in the sedation for the subarachnoid block, when they are discharged from the URPA, and at 6, 12, 24 h after the realization of the block, and end of effect after the realization of the block.
 - Need and rescue drugs: rescue analgesia will be scheduled for the hospitalization floor, in case it is necessary. The need, drug and time of administration regarding the realization of the blockade will be collected (Annex II).

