6.9. JUSTIFICATION OF SAMPLE SIZE

Taking into account the Pharmacokinetics of both local anesthetics, and previous studies(28, 29), using the G*Power program, the sample size is calculated. We consider significant a difference in the duration of the blockade of at least 3 h, with a deviation of 50%. The security level or alpha error is 5%. The beta error is 20%. A total of 108 patients were obtained, 54 in each of the lines of intervention, assuming 10% of losses.

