6.10. STATISTICAL ANALYSIS

A descriptive analysis of the variables collected will be carried out. Non-categorical ones shall be expressed as median +/- IQR (interquartile amplitude). Categorical variables shall be expressed as percentages or frequencies.

After performing the relevant normality tests (Kolmogorov-Smirnov or Shapiro-Wilk), the sample differences will be determined by t-Student or Mann-Whitney U tests. In the comparison of pain scales we will use the analysis of variance (ANOVA or Kruskal-Wallis).

The comparative analysis of the categorical variables will be carried out by means of Chi-square tests with cross tables.

The control of the possible intermediate and confusing variables will be carried out by means of Multiple Linear Regression Analysis.

The significance level will be, by default, 5% (p<0.05).

All calculations will be carried out with the statistical program SPSS[®] 25.0 for Mac.

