ANNEX III. DATA COLLECTION NOTEBOOK

Group	Levobupivacaine/Ropivacaine	
Hospital stay	In days	
Age	In years	
Sex	Female/Male	
Weight	In kg	
Size	In m	
Body Mass Index		
Type of Fracture	Subcapital/Petrochanteric/Subpетrochanteric/Other	
Type of Surgery	Partial athroplasty/Interlocking/Other	
Duration of Surgery		
On arrival at the operating room	EVN/Algoplus/Painad	
Latency time		
When sitting	EVN/Algoplus/Painad	
At Discharge of Resuscitation	EVN/Algoplus/Painad	
At 6 o'clock from the blockade	EVN/Algoplus/Painad	
At 12 o'clock of the blockade	EVN/Algoplus/Painad	
Within 24 hours of the blockade	EVN/Algoplus/Painad	
At the end of the blockade	EVN/Algoplus/Painad	
Analgesic rescue	Drug used	
Minutes to rescue	Time elapsed from lock to rescue	
Morphic equivalence	Equivalence in morphics of the rescue used	
Nausea and vomiting		
Toxicity	Toxicity developed by local anesthetics	
Delirium		
Infection	Clinically and analytically diagnosed	
Exitus		

BIBLIOGRAPHY

2. Tim JS Chesser DI, Antony Johansen, Alberto Belluati, Carlota Pari, Achile Contini, Stijn C Voeten, Johannes H Hageman, Kornelis J Ponsen, Nuria Montero-Fernández, Alberto Delgado-Martínez, Francisco Chana-Rodríguez Hip fractur systems-European experience. *OTA International.* 2020;3(1):1-6.
4. Fernández [name] M MJ, Olmos JM, [name]-[name] J, Hernández JL. Review of the incidence of hip fracture in Spain. *Rev Osteoporos Metab Miner.* 2015;7(4):115-20.

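### Better analgesic control has no deciding pain-score comparison: the plan permits about 18 unadjusted 5% tests, so the error rate of that secondary claim is well above 5%

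*Combined protocol and SAP*

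**What the plan says.** Section 3.1 gives the hypothesis three parts: levobupivacaine has advantages "since a better analgesic control, similar latency period, and a longer analgesic duration are obtained". Pain control is thus listed apart from duration.

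Section 6.7 lists the measurements as "Analgesic scales: EVN, Algoplus and PAINAD at rest and in activity". The occasions are arrival, the first 10 minutes after the block, sedation for the spinal, discharge from the recovery unit, 6, 12 and 24 h, and the end of effect. That is seven occasions after the block.

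The case report form in Annex III has six post-block rows: sitting, recovery discharge, 6, 12 and 24 h, and "At the end of the blockade". Each row has one entry per scale, with no split into rest and activity.

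For the analysis, section 6.10 assigns pain scales to ANOVA or Kruskal-Wallis and then states "The significance level will be, by default, 5% (p<0.05". It gives no key scale, time or condition, no order of testing, no adjustment and no repeated-measures model. Section 1.14 lists the pain scores as secondary. Sections 1.14 and 6.11 name one main endpoint, the duration of the block.

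**The concern.** A hypothesis about pain control needs a rule for when it counts as supported. Without one, a significant result on any scale at any time could be reported as better analgesic control, and the nominal 5% does not describe the risk that such a report is false. The trial is open (section 4) and the research team does the analysis (section 10), so nothing in the plan would prevent choosing the favourable comparison after the data are seen.

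A second issue concerns interpretation. The end-of-effect score is tied to the main outcome: a patient whose block lasts longer is scored later. Comparing arms on that row does not compare pain at a common time.

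**Working it through.** The plan states no number of pain-score tests and no overall error rate, so there is no figure to reproduce. The inputs are the 5% level (6.10), the scales, conditions and occasions (6.7) and the form rows (Annex III).

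**Number of tests the plan permits**
- Annex III: 3 scales x 6 post-block rows = 18.
- Section 6.7 read literally: 3 scales x 7 post-block occasions x 2 conditions = 42.
- Section 1.16 mentions a 48 h score that is in neither list. It would make these 3 x 7 = 21 and 3 x 8 x 2 = 48.

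The 42 is an upper reading. The form has no rest and activity fields and no score row for the first 10 minutes, only a latency time. Section 6.8 names only EVN and Algoplus when latency is explored. The working figure is therefore 18.

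**Independent tests, no true difference**

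Chance of at least one p<0.05 in k tests = 1 - 0.95^k.
- k = 18: 1 - 0.95^18 = 0.603
- k = 42: 1 - 0.95^42 = 0.884
- k = 3 (one test per scale): 1 - 0.95^3 = 0.143

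In the direction favouring levobupivacaine, 18 tests give 1 - 0.975^18 = 0.366, against a nominal 0.025.

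**Correlated tests**

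Scores on the same patients are correlated, so independence is the upper end. Correlated normal test statistics were simulated, with rejection when |Z| > 1.96. In the rows with separate values, the correlation between two tests is the product of the correlations for each factor on which they differ. All correlations are assumptions.

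| Assumed correlation | 18 tests, either direction | 18 tests, favouring levobupivacaine | 42 tests, either direction |
|---|---|---|---|
| None | 60% | 37% | 88% |
| Moderate: scales 0.7, times 0.4, conditions 0.7 | 43% | 22% | 66% |
| Strong: scales 0.9, times 0.6, conditions 0.9 | 29% | 15% | 41% |
| Common 0.5 for every pair | 40% | 20% | 59% |
| Common 0.7 for every pair | 28% | 14% | 38% |
| Common 0.9 for every pair | 15% | 8% | 19% |

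The nominal values are 5% in either direction and 2.5% in one. The lowest entries are about three times nominal.

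**End-of-effect row**

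This row supplies 3 of the 18 tests. Its timing does not raise the false-positive rate of those tests. The difficulty is what they estimate: the scoring time differs by patient and, if duration differs, by arm.

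**The case against.** The strongest reply is that nobody has committed to 18 tests. Section 6.10 sends two-group differences to the t or Mann-Whitney test and gives pain scales a separate ANOVA line. With two arms, that line could mean an analysis over time, or a comparison of the scales with each other, since validating them is a stated aim (2.1, 3.2.2). This stands: the count is what the plan permits, not what it announces. It does not remove the problem. The text does not say that the analysis is a repeated-measures one, Kruskal-Wallis has no repeated-measures form, and one overall test per scale still leaves three unadjusted tests.

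A reader might also infer more than the documents support:
- **That a false positive is likely.** For 18 tests the chance passes 50% only with weak correlation (51% at a common 0.3, 46% at 0.4), and three scales scored together on one patient are unlikely to be weakly correlated. In favour of levobupivacaine it stays below 50% even under independence.
- **That 42 tests will be run.** The form does not collect the data for them.
- **That the trial's main result is compromised.** The scores are secondary, and this multiplicity leaves the single duration comparison untouched.
- **That an end-of-effect comparison is meaningless or inflates error.** The documents do not define end of effect or commit to a between-arm test there. The score remains useful as description.

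**Conclusion.** The concern holds for the secondary claim of better analgesic control. No comparison is named as decisive and every permitted test is at an unadjusted 5%. On the 18-test schedule, the chance of at least one false positive is 60% under independence and about 43% to 29% under the assumed moderate to strong structures. In favour of levobupivacaine, the correlated figures are about 22% to 15%, against 2.5%. The figures depend on how many tests are run and on correlations that the documents do not give, but every scenario computed for 18 tests is well above nominal. The change should be made before the data are analysed. It is not a reason to doubt the duration comparison.

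**What to change.** In section 6.10, define better analgesic control by one prespecified summary per patient over the fixed 6, 12 and 24 h assessments, for example the mean of the three scores. Then choose one of two rules:
- name one scale and test its summary at 5%; or
- test the summary on each of the three scales with Holm's correction at an overall 5%. The smallest p is compared with 0.05/3 = 0.0167, the next with 0.025 and the last with 0.05.

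State whether the summary uses rest or activity scores, and label that field in Annex III. State how missing scores and scores after rescue analgesia enter it. Report all single-time scores as estimates with 95% CIs and no significance claim, and use end-of-effect scores only descriptively. Testing pain control only if duration is significant is optional.

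The cost is SAP wording and a small change to the form, with no extra patients or assessments. The downside is that a difference confined to one time or one scale can no longer be claimed as significant. That includes the score on sitting, which matters because section 2.3 ties efficacy to mobilising the patient; it would be reported as an estimate. If the sponsor does not want a formal claim, the lighter alternative is to label all pain scores exploratory and drop significance statements about them.

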6.11. ASSESSMENT OF EFFICACY

The main endpoint of the study's effectiveness will be the difference in the duration of the blockade.

6.12. POLICY REGARDING INTERMEDIATE ANALYSES AND CRITERIA FOR EARLY COMPLETION OF THE TRIAL.

This clinical trial may be stopped earlier than expected by the result of an interim analysis demonstrating greater than expected benefit or harm in any of the treatment arms. 1 formal internal efficacy and safety analysis will be carried out when 50% of the expected number of participants are reached. Poor study performance (e.g., slow patient recruitment, high rates of follow-up losses, or poor quality control) may be another cause of early study discontinuation.

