4. TYPE OF STUDY

A phase IV study of low level of intervention, open, prospective, randomized and controlled is proposed that aims to compare the analgesic efficacy of the proposed locoregional anesthetic techniques (PENG AND BNFCL) with two of the most frequently used local anesthetics in patients with hip fracture (Levobupivacaine and Ropivacaine) to whom surgical osteosynthesis (endomedullary interlocking or hip hemiarthroplasty) will be performed. The study begins in the preoperative period, applying an anesthetic protocol in the operating room and then followed up for at least 48 hours in the postoperative period.

The necessary sample size will be 108 patients, 54 patients per branch (Ropivacaine and Levobupivacaine). This figure could be increased to X patients in case of 10% losses due to complications during surgery.

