10. ANALYSIS AND COMMUNICATION OF RESULTS

The analysis of the data will be carried out by the research team and will be communicated in meetings and scientific articles in peer-reviewed journals. Regardless of the results of the study, the sponsor agrees to present them to the medical community through scientific publications, congresses or other means.

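### The half-way efficacy analysis can stop the trial for benefit but has no stopping boundary; testing at p<0.05 at both looks would give a type I error of about 8.3%, not 5%

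*Combined protocol and SAP*

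**What the plan says.** Section 6.12 plans a single interim look: "1 formal internal efficacy and safety analysis will be carried out when 50% of the expected number of participants are reached". It attaches a consequence to that look: "This clinical trial may be stopped earlier than expected by the result of an interim analysis demonstrating greater than expected benefit or harm" in either arm. The variable at stake is the primary one (section 6.11): "The main endpoint of the study's effectiveness will be the difference in the duration of the blockade".

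Two other places set an error level. Section 6.10 has "The significance level will be, by default, 5% (p<0.05", with no separate level for an interim or a final analysis. Section 6.9 has "The security level or alpha error is 5" per cent, with no mention of a second look. Neither section says whether the 5% is one- or two-sided.

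On conduct, section 4 describes the trial as open ("A phase IV study of low level of intervention, open, prospective, randomized and controlled is proposed"), and section 10 says "The analysis of the data will be carried out by the research team".

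**The concern.** A formal efficacy test that can end the trial in favour of one arm is a second opportunity for a false positive on the primary endpoint. To keep the overall rate at 5%, the plan must say how that 5% is divided between the looks. Nothing in sections 6.9 to 6.12 does so: there is no nominal interim level, boundary, spending function or adjusted final level, and the amount of benefit that would justify stopping has no number.

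Two things are at stake. First, the false-positive rate depends on a rule that could be settled after the interim data are known. The treatments are not masked, the research team does the analysis, and the available text describes no independent committee for the interim. Second, a trial stopped at half size because it crossed p<0.05 tends to overstate the difference in block duration, and that estimate would be the one published.

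**Working it through.** **Inputs from the plan.** One interim at 50% of participants (6.12); level 5% (6.9, 6.10); 54 per arm with 10% losses assumed, difference of interest 3 h, beta 20% (6.9); t test or Mann-Whitney test (6.10).

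**1. The plan's own figure.** With one final test at p<0.05 and no efficacy look, the type I error is 5% by construction. The question is what the interim adds.

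**2. Two looks at p<0.05.** Let Z1 and Z2 be the test statistics at 50% and 100% of the information. Under the null each is standard normal, with correlation √0.5 = 0.707. Then

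overall error = 1 − P(|Z1| < c1 and |Z2| < c2).

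With c1 = c2 = 1.960 the joint probability is 0.9169, so the error is 1 − 0.9169 = **0.0831**. This depends on neither the SD nor the sample size. If the look falls at 45% or 55% of the information, the error is 8.5% or 8.1%. With one-sided 5% at both looks it is 8.0%. Simulated t tests under the null (1,000,000 trials) give 8.36% for 24 then 49 per arm and 8.31% for 27 then 54 per arm.

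**3. Other interim rules, final test kept at two-sided 0.05.**

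| Interim rule for benefit | Overall type I error |
|---|---|
| p<0.05 | 8.3% |
| p<0.05 and observed difference above 3 h (SD 5.25 h assumed) | 7.1–7.6% |
| p<0.03 | 6.8% |
| p<0.02 | 6.1% |
| p<0.01 | 5.5% |
| p<0.005 | 5.2% |
| p<0.001 | 5.0% |

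With O'Brien-Fleming limits (2.797 at the interim, 1.977 at the end; p = 0.0052 and 0.0480) the overall error is 5.00%.

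**4. Illustration of stopping and overestimation.** This step needs an SD. Section 6.9 gives only a 50% deviation without saying of what, so the SD is an assumption. I took the SD that gives 80% power for 3 h with a two-sided t test (noncentral t, noncentrality 3 / (SD × √(2/n))). With 10% losses, 54 × 0.9 = 48.6, about 49 per arm, the SD is 5.25 h. With all 54 it is 5.51 h. Half of these numbers is 24 to 27 per arm.

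| Assumed SD | Trials stopped at an interim p<0.05, true difference 3 h | Mean estimate in stopped trials |
|---|---|---|
| 5.25 h | 49–54% | 4.0–4.2 h |
| 5.51 h | 45–50% | 4.2–4.4 h |

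The cause is visible in the critical difference. At SD 5.25 h with 24 per arm, the standard error is 5.25 × √(2/24) = 1.52 h. The t quantile on 46 degrees of freedom is 2.013, so only observed differences above about 2.013 × 1.52 = 3.05 h reach p<0.05. Every trial that stops therefore reports more than the true 3 h.

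**The case against.** The strongest reply is that the plan does not say p<0.05 applies at the interim. It asks for benefit beyond what was expected, and the planning difference is 3 h. If that meant a 95% confidence interval lying wholly beyond 3 h, the interim would need |z| of about 3.9 to 4.1 (24 to 27 per arm, SD 5.25 h), and the overall error would be 5.00%. Stopping is also optional: if the trial always ran to full size and no success were claimed at the interim, the final 5% test would not be inflated. Finally, the SD is not in the plan. At an SD of 6 h a p<0.05 interim would stop 40–44% of trials, fewer than shown above. Section 10 also does not say who carries out the interim.

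Much of this is fair. The 8.3% is conditional, and the honest range is about 5.0% to 8.3% depending on the rule. The stopping and overestimation figures are illustrations and do not carry the conclusion. But the confidence-interval rule appears nowhere in the plan. A reading just as natural, p<0.05 with an observed difference above 3 h, still gives 7.1–7.6%. An unnumbered phrase cannot bound the error, and p<0.05 is the only level written down. That stopping is optional does not help either, because the plan grants the option without limits. The small, low-intervention setting affects the consequences, not the gap.

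**Conclusion.** The concern holds. The plan provides for a formal efficacy look that can stop the trial for benefit, and nothing in it holds the two looks together at 5%. Using the default level at both looks gives 8.3% two-sided, or 8.0% one-sided. That result assumes a look at half the information and an unadjusted final test; it does not rest on any SD. Stricter interim rules bring the error down towards 5.0%, but the plan commits to none of them. This must be settled before the interim, because a boundary chosen after the data are seen controls nothing.

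**What to change.** Amend sections 6.10 and 6.12, before any interim data are seen, to state one numeric rule for stopping for benefit, the matching final level, and whether the tests are two-sided. Suitable choices are:

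- **O'Brien-Fleming:** two-sided p<0.0052 at the interim and p<0.048 at the end.
- **Haybittle-Peto:** p<0.001 at the interim and about p<0.05 at the end (5.02% overall if the final test is left at exactly 0.05).
- **Safety-only interim:** no efficacy test, and the final test stays at 5%.

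The cost is protocol wording, with no extra patients. With O'Brien-Fleming at SD 5.25 h (normal approximation), power falls from 80.7% to 80.5% with 49 per arm and from 84.4% to 84.1% with 54, a loss of about 0.3 percentage points. The real price is that early stopping for benefit becomes harder. At a true difference of 3 h, with noncentral t throughout, the chance of an interim stop falls from 49–54% to about 18–22% at SD 5.25 h, and from 45–50% to about 16–19% at SD 5.51 h.

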6.13. ASSESSMENT OF ADVERSE EFFECTS

6.13.1-DEFINITION OF ADVERSE EVENT:

An adverse event is defined as any event that occurs during the clinical study, whether it is either an intercurrent disease or accident, and that alters the well-being of the patient. The event may also take the form of a laboratory anomaly.

The term adverse event does not imply any causal relationship with the treatment of the study. All adverse events, including intercurrent diseases, will be reported and documented as described below.

Toxicities and adverse events shall be scored using version 5.0 of the CTCAE for reporting toxicity and adverse events.

https://ctep.cancer.gov/protocolDevelopment/electronic_applications/docs/CTCAE_v5_Quick_Reference_5x7.pdf

All participating researchers should have access to a copy of version 5.0 of the CTCAE.

6.13.2-CLASSIFICATION OF ADVERSE EVENTS:

Adverse events will be divided into the categories of serious and non-serious, which determine the procedure to be followed for the notification and documentation of the same.

a) Serious adverse events :

A serious adverse event is defined as anyone who threatens the life of the patient or causes death and also as one that causes disability, permanent disability or prolongs hospitalization. Any event involving congenital malformations or involving cancer is also serious.

b) Non-serious adverse events :

Adverse events that do not fall into any of the above categories will be classified as non-serious.

6.13.3-RELATIONSHIP WITH THE TREATMENT:

The investigator should try to explain each adverse event and assess its relationship with the trial treatment (probable, possible, unrelated). Criteria for establishing the relationship between clinical adverse reactions and study medication include:

3.1 *Likely*: If you meet the following three criteria:

- 1) There is a reasonable temporal relationship between the administration of the medicinal product and the adverse event.
- 2) The adverse event is a typical example of a known adverse drug reaction (If treatment is continued, the adverse event persists; if the drug is discontinued, the adverse event disappears; if a reexposure occurs, the adverse event reappears).
- 3) If there is another explanation of the adverse event (concomitant treatment, breakthrough disease), this explanation is less likely as the cause of the adverse event.

3.2 *Possible*: It is considered as an adverse reaction possibly related to the medication, one that meets the following two criteria:

- 1) There is a reasonable temporal relationship between drug administration and adverse event.
- 2) None of the criteria set out in point 2 above (probable) is met or there is another, more plausible explanation for the adverse event.

3.3 *Unrelated*: The adverse event will be classified as unrelated to the medication when it meets any of the following requirements:

- 1) There is no reasonable temporal relationship between the administration of the medicinal product and the onset of the adverse reaction.
- 2) The causal relationship between the medication and the adverse event is not biologically plausible.
- 3) There is another, more plausible alternative explanation for the adverse event.

4-Monitoring, reporting, and documentation of adverse events

-Non-serious adverse events

They will be recorded on the sheet dedicated for this purpose in the CRD of each patient, and no special notification procedure is necessary.

-Serious adverse events

All serious adverse events, regardless of their relationship to study treatment, should be reported as soon as possible, but no later than two working days. The *serious adverse event reporting form* should be sent to the study sponsor by email ([contact]).

Deaths and life-threatening events should be reported immediately by telephone or email to the trial sponsor. Subsequently, the AAG notification form will be sent by email. Preliminary notifications of AAG should be followed as soon as possible by means of detailed descriptions, including copies of clinical reports, autopsy reports and other documents requested by the sponsor. In both cases a follow-up of the AGAs must be completed (until they are resolved) as soon as possible, and a new completed AAG form faxed to the sponsor. It is very important that the AAG notification forms are as complete as possible from the time of the initial notification, including the investigator's assessment of causation. If the follow-up information changes the investigator's assessment of causality, it should be noted in the follow-up form. Any adverse events that the investigator believes are related to the treatment of the study should be reported to the sponsor, regardless of the time that has elapsed since the end of the study. It will be the obligation of the promoter to notify the AGAs in the terms and forms according to current legislation to the competent authorities, AEMPS, CC.AA and CEICs involved.

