1.14. STUDY VARIABLES

A. Main endpoint: duration of nerve block (analgesic efficacy of the two local anesthetics).

B. Secondary variables:

1. analgesia latency
2. duration of analgesia
3. adverse effects of the drugs used
4. scores of the analgesic scales: EVN, Algoplus, PAINAD.

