The adverse reaction profile of Ropivacaine is similar to that of other long-acting local amide-type anaesthetics and varies by route of administration. The most frequently reported adverse reactions, nausea and hypotension, are very common during anesthesia and surgery in general and it is not possible to distinguish those produced by the clinical situation from those caused by the drug or blockage. In addition, common adverse reactions of paresthesias, dizziness, headache, bradycardia, tachycardia, hypertension, vomiting, stiffness, back pain, urine retention, temperature elevation, and chills have been reported.

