There are no data in patients with renal impairment. It should be used with caution in debilitated patients, elderly patients or acute patients, and also in patients receiving antiarrhythmic drugs with local anaesthetic activity (e.g. mexiletine, or class III antiarrhythmic drugs) because its toxic effects may be additive.

Experience on the safety of treatment with Levobupivacaine for more than 24 hours is limited. The adverse reaction profile of Levobupivacaine is similar to that of other local amide-type anesthetics. Adverse reactions with local amide-type anesthetics are rare, but may occur as a result of overdose or unintentional intravascular injection and may be serious. Some adverse reactions reported are very common during anaesthesia and surgery in general and it is not possible to distinguish those caused by the clinical situation from those caused by the drug or blockage. The most commonly reported adverse reactions are nausea and vomiting, hypotension, dizziness, headache, fever, pain during the procedure, or back pain. Cases of prolonged weakness or sensory disorders, some of which have been permanent, have been reported associated with treatment with Levobupivacaine. It is difficult to determine whether the long-term effects were the result of drug toxicity or unnoticed trauma during surgery or other mechanical factors, such as catheter insertion and manipulation.

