6.8. ANESTHETIC PROTOCOL

- After giving informed consent to the patient or his guardian, the patient is monitored according to the usual standard (SEDAR Protocol, which includes ECG, TA, SatpO2).
- The ultrasound-guided block at the femoral level (PENG) is performed in the patient's transfer bed or table, depositing 20 cc of local anesthetic, with a 50-80 mm needle (depending on the anatomical characteristics) and a low-frequency probe. Next, a 50 mm needle and the high-frequency ultrasound probe will be used to block the NFCL by depositing 5 cc

of the same anesthetic, always without exceeding the maximum recommended dose for each drug. (See Annex I).

- Latency in the establishment of analgesia in the affected territory is explored, as well as an assessment of pain (Numerical Visual Scale and Algoplus).
- We proceed to the realization of the intradural spinal anesthesia, assessing again the pain that manifests. Subarachnoid blockade will always be performed with the same dose: 5 mg of Bupivacaine 0.5% hyperbaric with 10 µg of Fentanyl.
- After the surgical intervention, he will be transferred to the URPA (Post-Anesthetic Recovery Unit) and, subsequently, to the hospitalization floor when his situation allows it. At all times the constants, the analgesic variables and the treatments that you have needed will be recorded. (See Annex II).

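### Section 6.13.3 lets one adverse event be rated both possible and unrelated, and can leave another with no rating

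*Combined protocol and SAP*

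**What the plan says.** Section 6.13.3 of the combined protocol and SAP asks the investigator to assess each event's relation to treatment on three levels.

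- **Likely (3.1)** needs three things: reasonable timing; a typical known reaction to the drug; and, if another explanation exists, that "this explanation is less likely as the cause of the adverse event". The second carries a bracket on what happens when treatment continues, stops or is repeated, including: "if the drug is discontinued, the adverse event disappears; if a reexposure occurs, the adverse event reappears".
- **Possible (3.2)** needs two things: reasonable timing, and "None of the criteria set out in point 2 above (probable) is met or there is another, more plausible explanation for the adverse event".
- **Unrelated (3.3)** applies as soon as any one of three items is met: no reasonable timing, no biological plausibility, or "There is another, more plausible alternative explanation for the adverse event".

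No section says which rating prevails when two apply. Section 1.14 lists "adverse effects of the drugs used" as a secondary variable, and 3.2.2 includes describing the side effects of the combined technique. Section 2.2.1 says of nausea and hypotension, ropivacaine's most often reported reactions, that "it is not possible to distinguish those produced by the clinical situation from those caused by the drug or blockage". Section 2.2.2 says of some levobupivacaine reactions that "it is not possible to distinguish those caused by the clinical situation from those caused by the drug or blockage".

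**The concern.** A rating rule should send each event to exactly one category. Here the same clause, a more plausible other cause, admits an event to two categories with opposite meanings. Two investigators following the text faithfully could file the same well-timed event as possibly drug-related or as unrelated. The study is open (section 4), so that choice can be made with the arm known.

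There is a second fault. Likely requires any rival explanation to be less likely, while possible and unrelated refer to one that is more plausible. A typical reaction with an evenly balanced rival is not clearly placed.

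At stake is the meaning of the causality rating and of any account of drug effects that relies on it.

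**Working it through.** The documents give no figure to reproduce, so the check is one of logic.

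**Inputs, all from 6.13.3.** T: timing is reasonable. K: typical known reaction. B: link biologically plausible. A: other explanation is none, less, equally or more plausible.

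**Rules as written.**
- Likely = T and K and A is none or less.
- Possible = T and (not K, or A is more).
- Unrelated = not T, or not B, or A is more.

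**Cases with T and B both true (2 × 4 = 8).**

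| Other explanation | Typical reaction | Not typical |
|---|---|---|
| none | likely | possible |
| less plausible | likely | possible |
| equally plausible | no rating | possible |
| more plausible | possible and unrelated | possible and unrelated |

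Five cells have one rating, two have two, and one has none: 5 + 2 + 1 = 8.

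**All 2 × 2 × 2 × 4 = 32 combinations.** The 16 with T false are unrelated only. The 8 with T true and B false give 1 single and 7 double ratings, because implausibility makes them unrelated while 3.1 or 3.2 may also be met. Adding the 8 above: single 16 + 1 + 5 = 22, double 7 + 2 = 9, none 1.

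**The bracket in 3.1.** Section 6.8 gives the block once (20 cc plus 5 cc), so stopping and re-exposure cannot be observed. If the bracket therefore counts as failed, K is always false and only the right-hand column remains. The unrated cell becomes possible and no event can be likely, but the overlap stays. If the bracket only illustrates a typical reaction, the unrated cell stands.

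**Where 2.2.1 and 2.2.2 fit.** Causes that cannot be told apart are most naturally read as equally plausible. That is the third row, the gap, and not the fourth row, the overlap.

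**Size.** Suppose likely and possible together count as related, and let E be the number of events so counted when overlap events are rated possible. If a share s of them lies in the overlap, the related count is E on that reading and E(1 − s) when they are rated unrelated. The documents give neither E nor s. With E = 20 assumed, the counts are 20 v 20 at s = 0, 20 v 15 at 25%, 20 v 10 at 50% and 20 v 5 at 75%. This restates the assumption and does not estimate an effect.

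**Proposed order, same 8 cases.** Unrelated if any item of 3.3 holds: 2 cases. Otherwise likely if all of 3.1 holds: 2. Otherwise possible: 4. Each case gets one rating, and the other 24 combinations are all unrelated.

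**The case against.** The strongest reply is that little in the plan depends on the rating. Section 6.10 plans no table by causality, and no section says which ratings count as related. In Annex III the rows for nausea and vomiting, delirium, infection and death have no causality field, and the toxicity row is not tied to the 6.13.3 grades. The protocol also uses adverse effects loosely, so the all-cause record could satisfy the secondary variable. All of this stands and limits the consequence. It does not remove the contradiction, because 6.13.3 still asks for a rating and the serious-event form must carry a causality assessment.

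It can also be said that 6.13.3 guides judgement, and that 3.3, which states that events meeting any item will be classed as unrelated, controls. That is arguable but nowhere stated, and the fix makes it explicit.

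The unrated case depends on admitting an equally plausible level. With only none, less and more, no combination goes unrated. The level is nevertheless a real possibility, and sections 2.2.1 and 2.2.2 describe something close to it.

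A reader might infer from those two sections that the overlap is common. They do not support this, for the reason given in the working. Nor does the spinal: "Subarachnoid blockade will always be performed with the same dose" (section 6.8) means every patient has another possible cause, but nothing ranks it as the more plausible one.

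**Conclusion.** The point holds as an internal contradiction in 6.13.3, with an unrated case that depends on how the bracket in 3.1 is read. The causality rating, and any description of drug-related adverse effects based on it, is not uniquely defined. It rests on the text as printed, which reads as a translation but contains both clauses in full.

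It is a minor correction to a descriptive safety item. A reader might infer that the related count will differ widely between readings. The documents do not support that, since they give no event rate and no share of events in the overlap, and the share could be nil.

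A reader might also infer that safety reporting or early stopping is compromised. Serious events are reported whatever their cause, all-cause counts do not use the rating, and the main endpoint is the duration of the block. Reporting after the study ends turns on what the investigator believes, not on a 6.13.3 grade. Section 6.12 plans one interim efficacy and safety analysis but does not say that it uses attributed events.

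**What to change.** 1. In 6.13.3 add: *Rate in this order: unrelated if any criterion in 3.3 is met; otherwise likely if all three criteria in 3.1 are met; otherwise possible.*
2. Replace criterion 2 of 3.2 with: *the event is neither unrelated (3.3) nor likely (3.1).* Removing only its second half would leave 3.2 at odds with the order.
3. In 3.1 delete the bracket on continuing, stopping and re-exposure.
4. Report all-cause adverse events by arm beside the related counts, with related defined as likely or possible.

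The cost is a few lines of wording and one reporting line, with no new data, visit or procedure. Any event already rated should be checked against the order.

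The downside is that events with a more plausible other cause go to unrelated, which lowers the related count; the all-cause line keeps them visible. Deleting item 3 of 3.3 would also remove this overlap and would give the higher count. The order is preferred because it follows the stronger wording already in 3.3, and because it also settles the well-timed but biologically implausible cases.
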